#### **4.3.2 Dexcom® G5 Continuous Glucose Meter**

The CGM is used to collect interstitial glucose measurements on a continuous basis. The source data is stored in the cloud-based portal Dexcom CLARITY and outputted as .csv. The Sponsor Study Specific Procedure-001 and Study Specific Procedure-003 define the process for collecting this data and cleaning it to assure integrity. The metrics collected for analysis are as follows:

- Date and Time of Reading, Event Type (EGV or Calibration reading), and Glucose Value (in mmol/L).

Glucose Values for this device are only recorded in the range of 2.2-22.2 mmol/L. Values less than 2.2 will be recorded as "Low" and values greater than 22.2 will be recorded as "High."

#### **4.3.3 Blood Glucose Meter: Bayer® Contour Next One**

The BGM is used to collect blood glucose values during exercise sessions and to confirm blood glucose levels indicated by CGM. These data are being transferred by the Sponsor to the CRO. Variables included in this transfer are:

Date and Time of Reading to 1-minute precision, Blood Sugar (in mmol/L), and Control (binary indicator of whether the reading was a controlled calibration). Control readings will be excluded from analysis.

#### **4.3.4 Duplicate Timestamps:**

Some of the reports collected from the wearable devices are related to a specific timestamp.

Upon routine data management review, it has been identified that some reports contain duplicate timestamps and therefore have multiple results tied to one unit of time. Whenever duplicate timestamps are encountered in analysis, the mean of all duplicate instances will be calculated and used as the result at that given timestamp. The mean result will be rounded to as many decimals as the original data.

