10.4. Visit 5 Through 10 – Outpatient Stage

10.4.1. Visits 5 Through 10 – Treatment Day 4-113

During the outpatient stage, subjects will return for clinic visits every two weeks. Activities to be performed at these visits are outlined in the Schedule of Activities ([Table 1](#)[bookmark7](#)).

In the outpatient setting, subjects will perform moderate to high intensity aerobic exercise with a target of at least 2-3 qualifying sessions per week. To be eligible for study drug dosing, the planned aerobic exercise will be 30-75 minutes in duration. Additionally, the subject's BGM must range between 100-180 mg/dL (5.56 – 10 mmol/L) before the exercise session. Subjects must record their carbohydrate intake (eg, both dextrose tabs and carbohydrates from food) 15 minutes before exercise, during the exercise session, and up to 5 hours post-exercise session.

During the exercise session, the subject is to only drink carbohydrate free liquids (e.g., Powerade Zero or comparable product) and will be provided with glucose tabs to use as needed. The subject will take 5 BGM measurements with exercise: at -15 minutes and just before exercise to establish baseline value, at 30 minutes into the exercise session, at the end of the exercise session, and at 30 minutes after the exercise session. There is a ± 2 minute window on all of these time points.

Per ADA guidelines, if a subject's glucose falls to ≤ 70 mg/dL (3.89 mmol/L) during any exercise session, then the exercise session should be stopped, and no more exercise should be completed that same day; the subject should rest, and glucose tabs should be taken every 15 minutes until the hypoglycemia is corrected and euglycemia (confirmed by BGM) is maintained. Subjects will be provided with a supply of glucose tabs and instructed to use these rather than other sources of carbohydrate to treat hypoglycemia.

During the outpatient phase the subject will be provided with the following items for recording study data and will be provided with instructions for use and uploading data to the cloud if applicable.

1. Blood Glucose Meter: Bayer[®] Contour Next One
 - a. Used to collect blood glucose values during exercise sessions and to confirm blood glucose if a value ≤ 70 mg/dL (3.89 mmol/L) is indicated by CGM.
2. Dexcom[®] G5 Continuous Glucose Meter
 - a. Used to collect interstitial glucose measurements on a continuous basis.
3. Fitbit[®] Ionic

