### 4.3 Wearable Monitoring Devices

There are three wearable devices used for collection and analysis of metrics related to the study endpoints. Each subject has data collected from a wearable fitness tracker (Fitbit Ionic), continuous glucose meter (CGM), and a blood glucose meter (BGM). Endpoint Analysis will require confluence of data from these sources and therefore understanding of each is imperative.

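### SAP 4.3.4 averages same-minute meter readings before the 70 mg/dL threshold is applied, so a low reading that counts toward the primary endpoint can be erased but never created

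*SAP*

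**What the plan says.** SAP 4.3 lists three devices that feed the endpoints: the Fitbit, the CGM and the BGM. SAP 4.3.3 describes the BGM transfer as "Date and Time of Reading to 1-minute precision", with glucose in mmol/L, and the only readings it removes are calibration checks: "Control readings will be excluded from analysis".

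SAP 4.3.4 covers the device data together. It reports that "it has been identified that some reports contain duplicate timestamps", without naming the device. Its rule is that "the mean of all duplicate instances will be calculated and used as the result at that given timestamp", and then: "The mean result will be rounded to as many decimals as the original data". It applies whenever duplicates are met in analysis and contains no exception for the BGM.

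The primary endpoint (SAP 3; Protocol 5.2.1) is hypoglycemia by BGM, at or below 70 mg/dL (3.89 mmol/L). SAP 4.3.6 ties an event to a session if it occurs during exercise or within 30 minutes of its end. SAP 3 restricts the primary analysis to qualified sessions of 30 to 75 minutes. On conduct, Protocol 10.4.1 says that if glucose falls to that threshold during a session, "then the exercise session should be stopped, and no more exercise should be completed that same day".

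**The concern.** A mean is a sensible way to merge duplicate values in a continuous stream. It suits a threshold event badly, because the event is defined by a single reading crossing a line and the mean can move it back. Neither document says that the threshold is applied to raw readings first, that the lowest duplicate is kept, or that a session stopped for a low counts as an event whatever the merged value. The same two readings can therefore be scored as an event or as no event depending on whether the clock minute changed between them. Where that happens, the analysis can record no hypoglycemia for a session in which the subject saw a low reading and was required to stop.

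**Working it through.** **1. Does the rule reach the primary endpoint?** Yes. The BGM is one of the devices in SAP 4.3, the rule in 4.3.4 is general, and only control readings are dropped. Two ordinary BGM readings in one clock minute are duplicates by construction.

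**2. Apply the rule in the units of the data.** Threshold: 3.89 mmol/L. The number of decimals is not stated; I assume one, with half-up rounding.

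| Two readings, same minute | Mean | Rounded | Scored under SAP 4.3.4 | Scored one minute apart |
|---|---|---|---|---|
| 3.7 and 4.1 | 3.90 | 3.9 | no event | event |
| 3.5 and 4.3 | 3.90 | 3.9 | no event | event |
| 3.8 and 4.0 | 3.90 | 3.9 | no event | event |
| 3.8 and 3.9 | 3.85 | 3.9 | no event (rounding alone) | event |
| 3.5 and 4.1 | 3.80 | 3.8 | event | event |

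The smallest second reading that erases a low is 3.9 for a low of 3.8, 4.0 for 3.7, 4.2 for 3.5, 4.4 for 3.3 and 4.7 for 3.0. Lows near the threshold are easily lost; deep lows need a large disagreement. With two-decimal data the averaging effect remains, but the rounding loss in the fourth row does not.

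**3. Direction.** If every reading in a minute is above the threshold (3.9 or higher at one decimal), so are their mean and its rounded value. Averaging cannot create an event.

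**4. When the session's score changes.** I score a session as hypoglycemic if it has at least one low. The session must last at least 30 minutes, because a shorter one is not qualified and leaves the primary analysis. No other BGM reading during exercise or in the 30 minutes afterwards may be low. The scheduled readings in that window (Protocol 10.4.1) are at 30 minutes, at the end of exercise and 30 minutes later.

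**5. Size of one lost event.** Two to three sessions a week for 12 weeks is 24 to 36 sessions. On an events-per-session scale, one lost event changes a subject's rate by 100/36 = 2.8 to 100/24 = 4.2 percentage points. The mean of a 14-subject arm changes by 2.8/14 = 0.20 to 4.2/14 = 0.30 points.

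**6. Power.** First, the plan's own figure. The effect size is 59/15² = 0.262. For a one-way ANOVA with three groups and alpha 0.05, the noncentrality is 3n × 0.262. This gives 78.9% at n = 13 and 82.3% at n = 14, so 14 per arm is reproduced.

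If a share q of events is lost equally in every arm, the differences between means shrink by (1 − q) and the effect size becomes 0.262 × (1 − q)². Holding the SD at 15 and n at 14:

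| Share lost (assumed) | Power |
|---|---|
| 0 | 82.3% |
| 1% | 81.5% |
| 2.5% | 80.2% |
| 5% | 78.0% |
| 10% | 73.2% |

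The documents give no value for q. As one illustration, if 2% to 5% of lows were retested within the minute and half of those pairs averaged above the threshold, q would be 0.02 × 0.5 = 1% to 0.05 × 0.5 = 2.5%.

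**The case against.** The strongest reply is that nothing shows this ever happens. SAP 4.3.4 speaks of duplicates in some reports, and within SAP 4.3 the outputs called reports are the Fitbit's. No passage calls for a second BGM reading in the same minute as a low. The repeats that are described are pre-exercise checks, which fall outside the event window; a BGM check prompted by a CGM low; and rescue repeated at 15-minute intervals, where a recheck would carry a different stamp. All of that stands, and it is why the frequency must be called unknown.

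A reader might infer three stronger things that the documents do not support:

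- **That the rule acts mainly on events**, because people retest when they see a low. This is plausible, but no passage says it.
- **That it removes events selectively by arm.** The rule ignores treatment. An arm with more lows would lose more in absolute terms if the lost share were equal, but that is proportional attenuation, not a differential loss.
- **That any session stopped for hypoglycemia can be scored event-free.** A session stopped before 30 minutes is excluded as unqualified, and another low in the window would still capture the event.

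It can also be argued that two readings in one minute are replicates, so their mean is the better estimate of glucose, while letting one low decide leans the other way. That is fair for estimating a level. It does not explain why the same pair one minute apart is scored as an event.

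**Conclusion.** The point holds as a gap in the SAP of low severity. As written, the duplicate rule conflicts with a threshold endpoint: it can remove a primary event, cannot add one, and makes scoring depend on a clock boundary. It matters only for same-minute, non-control BGM pairs that straddle the threshold, in qualified sessions with no other low in the window.

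The effect is probably small. At an assumed loss of 1% to 2.5%, power stays above the planned 80%; on the same assumptions it would be below 80% at a loss of 5%. These figures rest on equal proportional loss in each arm, an SD of 15, 14 analysed subjects per arm and an events-per-session rate. The rounding component also depends on one-decimal data.

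**What to change.** Amend SAP 4.3.4 in one sentence: limit averaging of duplicates to the CGM and heart-rate streams and to continuous summaries; for the primary endpoint, compare each raw non-control BGM reading with the threshold of 70 mg/dL (3.89 mmol/L) before any averaging or rounding.

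Before unblinding, count the BGM duplicates, and those that straddle the threshold, without reference to treatment. Report that count with mean-based scoring as a sensitivity analysis. A count of zero would settle the matter.

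The cost is the sentence, the count and one rerun of the primary table. The sample size does not change. The downside is that an occasional false low retested within the minute will count as an event, as it already would if the two readings were one minute apart.

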### **4.3 Statistical Methods and Data Analysis**

#### **4.3.1 Disposition**

The number and percentage of screened subjects, screen failures, subjects who entered the CRC phase, completed the CRC phase, and subjects included in each of the study populations will be summarized using the ITT population for CRC phase.

The number and percentage of subjects who entered the Outpatient phase, completed the Outpatient phase and subjects included in the various study populations will be summarized using the ITT population for Outpatient phase.

The number and percentage of subjects who prematurely discontinued from the CRC Phase along with reasons for study discontinuation will be summarized by last treatment received using the ITT population for CRC phase.

The number and percentage of subjects who prematurely discontinued from the Outpatient phase along with reasons for study discontinuation will be summarized by last treatment received using the ITT population for Outpatient phase.

For all subjects, analysis population inclusions, disposition and reason for discontinuation will be listed for both CRC and Outpatient phase.

A listing of the subject eligibility (inclusion/exclusion met/not met, reasons for screen failure) at CRC phase will be provided.

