- b. Subjects will be instructed not to exercise between Visit 2 and Visit 3.
- c. Questionnaires to be completed are Barriers to Physical Activity Diabetes (Type 1) (BAPAD-1), Hypoglycemia Fear Survey (HFS) and Hypoglycemia Confidence Scale (HCS).
- d. CGM will be placed approximately 24-48 hours prior to data collection at CRC Visit 2.
- e. Collection timepoints  $\pm$  2 minutes are: -15 minutes, 0 minutes (just before initiation of exercise), and at 15, 30, 45, 60 and 75 minutes after initiation of exercise.
- f. Follow-Up occurs 14 days after the last exercise period.
- g. An immunogenicity sample will be drawn before the first dose of investigational product, every four weeks (28 days  $\pm$  2 days) and at the End of Study visit.
- h. CGM data will be downloaded.
- i. During the CRC Phase of the study, subjects will perform moderate-to-high-intensity exercise of at least 45 minutes duration, with each exercise session separated by at least 2 days during the inpatient phase of the study. During the Outpatient Phase of the study, subjects will be asked to maintain a weekly exercise average of 2 to 3 sessions weekly of at least 30 minutes. Exercise data will be downloaded from the wearable device. Data include heart rate, calories burned, daily steps, floors climbed, distance covered, active minutes.
- j. BGM Measurements will be performed at the following timepoints during CRC visits,  $\pm$  2 minutes:
  - -15 minutes (both YSI and BGM)
  - Time 0 (immediately before exercise) (both YSI & BGM)
  - 15 minutes (YSI only)
  - 30 minutes (both YSI & BGM)
  - 45 minutes (both YSI & BGM, end of exercise)
  - 60 minutes (YSI only)
  - 75 minutes (both YSI & BGM, thirty minutes after completion of exercise)
- k. BGM data will be downloaded at each patient visit.
- l. Investigational Product (IP) for first outpatient visit will be dispensed at the end of visit 4.
- m. Subject will wear both Fitbit Ionic and Polar Beat H10 heart rate sensor during this visit.
- n. Subject will wear only the Fitbit Ionic during these visits.

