#### 1.3.1 Randomization and Blinding

The study statistician will create the randomization schedule for the study. The randomization assignment for the subject will be conducted once at the time of enrollment and confirmation of eligibility. The CRC assignments will be by random assignment during the first session to either Glucagon RTU or Placebo. At the second session, the subject will be crossed over to the other treatment assignment. At the completion of the CRC visits, the subject will then have his/her treatment assignment applied for the parallel group study.

The cross-over study is blinded to the extent possible since all subjects will receive both Glucagon RTU and placebo. All staff, subjects and study team members will know that the subject will receive both study treatments during the CRC sessions. During the outpatient study, two of the treatments will be blinded to the study staff, subjects and Sponsor. One arm of the study will be open label. It is imperative for the study staff to remain blinded to treatment assignment prior to randomization and during the study treatment periods as not to bias the outcome.

Glucagon RTU and Placebo will be prepared and administered so that the two will be indistinguishable.

Blinding of study treatment is critical to the integrity of this clinical trial. It is expected that in the majority of cases, AEs can be properly managed without the need for unblinding. However, in the event of a medical emergency in which knowledge of an individual subject's treatment

assignment is considered critical to the subject's management, the treating physician may unblind the treatment assignment. The investigator should contact the responsible Medical Director to discuss the subject and circumstances requiring the unblinding. The blind will be broken only for the specific subject under discussion. The Sponsor will remain blinded to the treatment assignment. Every effort will be made to restrict knowledge of the treatment assignment to the investigator only.

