### **2.3 Treatment Group Labelling in TFLs:**

The Treatments in the CRC phase will be labelled as “Treatment A” and “Treatment B”

The Treatments in the Outpatient phase will be labelled as “Treatment A,” “Treatment B,” “Treatment C” in the footnote for the respective TFLs. A Footnote will be added for the treatment columns as below:

“Treatment A” = “Glucagon RTU (30 µL active - 0.15 mg) with 50% insulin pump reduction”

“Treatment B” = “Placebo injection (30 µL vehicle) with 50% insulin pump reduction”

“Treatment C” = “Glucagon RTU (30 µL active - 0.15 mg) without 50% insulin pump reduction”

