## 4. STATISTICAL METHODOLOGY

### 4.1 Definition of Analysis Population

**All Screened Subjects:** All Screened subjects will include any subject who signed the informed consent form.

**Intention to Treat (ITT) Population:** All randomized subjects regardless of whether they received Study Drug.

**Per Protocol (PP) Population:** ITT participants who completed a qualified exercise session, and who was dosed within the study window and did not meet any of the key exclusion criteria at screening. The definition of qualified exercise is defined in Section 2.4.

**Safety Population:** All randomized subjects who received any amount of Study Drug.

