#### **4.3.9 Safety Analysis**

##### **Adverse Events:**

All analyses will be conducted in the safety population. Adverse events will be recorded from the time of consent until completion of study. The number and percentage of subjects with AEs will be displayed by body system and preferred term (MedDRA), by study treatment. Summaries in terms of severity and relationship to Study Drug will also be provided. All SAEs will be summarized in a similar manner. Participant listings of all AEs causing discontinuation of study medication and SAEs will be produced.

All AEs will be listed for individual subjects showing both verbatim and preferred terms. Separate summaries of treatment emergent SAEs and TEAEs related to Study Drug will be generated.

AEs will be summarized separately during the CRC treatment visits. Any AE that occurs after administration of study drug at Visit 3 and prior to administration of the alternate study drug at Visit 4 will be treatment emergent with respect to the study drug received at Visit 3. Any AE that occurs after administration of study drug at Visit 4 and prior to the first administration of study drug in the out-patient phase will be treatment emergent for the study drug received at Visit 4. Any event reported on the eCRF that occurs at the time of or after the initiation of Study Drug in the out-patient phase is defined as treatment-emergent for that study drug. Additionally, an AE that was reported to have started on Day 1 without an associated onset time is assumed to have

occurred after the initiation of Study Drug. Hence, AEs occurring on Day 1 with no associated onset time are assumed to be treatment emergent.

SAEs associated with a protocol specified procedure and occurring after the time of consent but before administration of first dose of Study Drug are defined as Non-Treatment Emergent AEs (NTEAE).

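### SAP 4.3.1 groups outpatient discontinuations by last treatment received, so a subject randomized to the open-label arm who leaves before the first outpatient dose can never be counted under that arm

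*SAP*

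**What the plan says.** SAP 4.3.1 (Disposition) has parallel sentences for the two phases. For the Outpatient phase it says that "reasons for study discontinuation will be summarized by last treatment received using the ITT population for Outpatient phase". SAP 4.1 defines the ITT population as "All randomized subjects regardless of whether they received Study Drug".

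On timing, SAP 1.3.1 says: "The randomization assignment for the subject will be conducted once at the time of enrollment and confirmation of eligibility". The schedule of activities places randomization at Visit 3. The outpatient arm takes effect later: "At the completion of the CRC visits, the subject will then have his/her treatment assignment applied for the parallel group study". Outpatient training is at Visit 4, and a footnote to the schedule adds: "Investigational Product (IP) for first outpatient visit will be dispensed at the end of visit 4".

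SAP 2.3 names the treatments. A is glucagon with the 50% pump reduction, B is placebo with the reduction, and C is glucagon without it. Only A and B are given in the CRC phase. I use the SAP letters throughout; the protocol schema (section 2.2) has A and B the other way round.

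**The concern.** The discontinuation table is the planned summary of who left and why. It has to show drop-out by arm because SAP 2.2 rules out imputation. A subject with no outpatient dose also has no qualified session under SAP section 3, and so contributes no rate to the three-arm ANOVA. Such a subject disappears from the primary comparison, and the reader needs to see which arm lost them.

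Between the end of Visit 4 and the first outpatient dose, a subject already belongs to an outpatient arm but has received only crossover treatments. Arms A and B are blinded and arm C is open-label, so C is the arm where a known assignment could influence whether a subject starts. It is also the one arm to which this rule can never attribute an undosed leaver.

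**Working it through.** **1. Who is affected.** The outpatient stage is parallel, with one treatment per subject. After one outpatient dose, the last treatment received is the randomized arm, barring a dosing error. Only subjects who leave between the application of the outpatient assignment and the first outpatient dose can differ.

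**2. Where such a subject goes.** Two readings are open.

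- *Literal reading.* The last treatment received is the Visit 4 drug, which is A or B. The adverse-event rule in SAP 4.3.9 treats the same interval this way: an event after the Visit 4 dose and "prior to the first administration of study drug in the out-patient phase will be treatment emergent for the study drug received at Visit 4".
- *Outpatient-only reading.* Last treatment means last outpatient treatment, or the subject is held not to have entered the Outpatient phase, a term that SAP 4.3.1 uses without defining. The subject then has no column.

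C is not given in the CRC phase, so on both readings an undosed subject randomized to C adds nothing to C.

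**3. The plan's own figures.** There is no stated figure for this rule, but the arm size comes from the sample-size paragraph (SAP 1.3), which reproduces. The squared effect size is 59/15² = 0.262. The noncentral F calculation for three groups at alpha 0.05 gives power 0.789 with 13 per arm and 0.823 with 14, so 14 per arm, or 42 in all. For attrition, 42 × 1.15 = 48.3, against 42/0.85 = 49.4 (50 rounded up); the plan randomizes 48. At 1:1:1 that is 48/3 = 16 per arm.

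**4. Size per subject.** One undosed leaver randomized to C is 1/16 = 6.25 percentage points of arm C by randomized arm, and 0 under the SAP rule.

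**5. Illustrations.** The numbers of leavers below are assumed, because the documents give none. The denominator is 16 per column. For the literal reading, the Visit 4 drug is assumed to split evenly, so each leaver adds an expected 0.5 to A and 0.5 to B.

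| Undosed leavers (assumed) | By randomized arm, A / B / C | Literal reading, expected A / B / C | Outpatient-only reading, A / B / C |
|---|---|---|---|
| 1, from C only | 0 / 0 / 6.25% | 3.1 / 3.1 / 0% | 0 / 0 / 0 |
| 3, from C only | 0 / 0 / 18.75% | 9.4 / 9.4 / 0% | 0 / 0 / 0 |
| 1 per arm | 6.25% each | 9.4 / 9.4 / 0% | 0 / 0 / 0 |
| 2 per arm | 12.5% each | 18.75 / 18.75 / 0% | 0 / 0 / 0 |

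For example, one leaver per arm is 3 in all, so 1.5 are expected in each of A and B, and 1.5/16 = 9.4%. Two per arm is 6 in all, which equals the whole allowance of 48 − 42 = 6.

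**The case against.** The strongest reply is that the scope is narrow and the information is not lost. Much of this stands.

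- *The table is right for nearly everyone.* A reader might infer that the whole outpatient discontinuation table is built on the wrong grouping. It is not: for every subject dosed as an outpatient, the grouping equals the randomized arm, barring dosing errors.
- *Charging the Visit 4 drug is an inference.* SAP 4.3.1 does not spell it out, and the rule in SAP 4.3.9 concerns adverse events, not disposition. A reader might conclude that drop-out in A and B will be overstated, or that a fixed share of undosed leavers will be misplaced. Both depend on the literal reading and an even Visit 4 split. On the outpatient-only reading, A and B lose their undosed leavers too.
- *No number is given.* The 15% attrition in SAP 1.3 is not split by phase, and no rate of leaving before the first outpatient dose is stated. That open-label subjects would decline to start is conjecture.
- *Other outputs show these subjects.* SAP 4.3.1 says: "For all subjects, analysis population inclusions, disposition and reason for discontinuation will be listed for both CRC and Outpatient phase". SAP 4.3.3 lists dosing, with a comment where a dose was not given. With 48 subjects these listings can be read by hand. The counts of subjects who entered and completed the phase may also help, but entry is undefined and the grouping is not stated.
- *Shared letters are defensible.* CRC treatments A and B are the same interventions as outpatient A and B, and the table titles name the phase.

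What does not fall away is that the summary table states a grouping rule under which an undosed arm C leaver cannot appear under C. A listing allows a reader to repair that count but does not correct the table.

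**Conclusion.** The concern holds within a narrow scope. A stated rule, applied to a population defined by randomization, can give a wrong count of drop-out by arm. It does so only for subjects who leave after the outpatient assignment is applied and before the first outpatient dose. For the open-label arm the direction is certain on either reading: the count can be too low and never too high from this cause. Each such subject is worth 6.25 percentage points, assuming 16 per arm. How many there will be is unknown, so the total effect cannot be stated.

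A reader might also infer that the primary result is biased by this rule. The documents do not support that: the rule governs a descriptive table, and the primary test, the 48 subjects and the power do not depend on it. The correction is worth making because, without imputation, this table is where a reader would look for differential drop-out.

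**What to change.** In SAP 4.3.1, summarize outpatient discontinuations and their reasons by randomized outpatient arm. Add a separate row for subjects randomized but not dosed in the Outpatient phase. Define entry to the Outpatient phase so that these subjects are counted, for example from the point at which the outpatient assignment is applied. Last treatment received may stay as the grouping for CRC-phase discontinuations.

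While editing, align the population: the text of SAP 4.3.1 names ITT, but the title of Table 14.1.1.2 names all screened subjects. Separate letters for CRC and outpatient treatments are optional.

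The cost is a sentence or two in the SAP, one row and a column header in the table shell. No new data, patients or change to the primary analysis are needed.
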